2 SUMMARY OF RATIONALE

a) MDS and AML in relapse after allo hematopoietic stem cell transplantation and their current treatment
Among patients with acute myeloid leukemia (AML), allogeneic hematopoietic stem cell transplantation (allo-HSCT) used as post-remission therapy for those with high-risk molecular profiles or as salvage therapy for those with resistant disease offers the highest potential for long-term survival[1]. In addition, allo-HSCT is the only curative option for patients with myelodysplastic syndromes (MDS) and chronic myelomonocytic leukemia (CMML)[2]. Still, relapse after allo-HSCT remains the major cause of treatment failure and is associated with a dismal prognosis[3]. Treatment options for those patients are mainly restricted to chemotherapy, donor lymphocyte infusions (DLI) or second allo-HSCT [4]. Treatment approach should ideally offer efficient antileukemic activity, acceptable toxicity and mechanisms to direct the donor immune system towards an enhanced graft-versus-leukemia effect without provoking graft-versus-host disease (GvHD). To fulfil all criteria, combination of azacitidine (AZA) to donor lymphocyte infusion (DLI) could be used in patients with relapse inferior to 2 years after allo-HSCT. AZA is approved for the treatment of patients with high-risk MDS and AML [5, 6]. Beyond its direct cytotoxic effects and ability to induce remissions even in patients refractory to chemotherapy, AZA is considered to increase the immunogenicity of AML blasts by re-expression of important antigens[7-9]. Furthermore, animal models suggest an immunomodulatory role of AZA that might attenuate GvHD after DLI [10, 11]. Combination was evaluated in AZARELA trial [12]. Treatment schedule contained up to eight AZA cycles (100 mg/m²/day, days 1–5, every 28 days) followed by DLI (from 1–5 x 10⁶ to 1–5 x 10⁸ CD3 cells/kg) after every second AZA cycle. A median of three courses AZA (range 1–8) were administered and 22 patients (73%) received DLI. Overall response rate was 30%, including seven complete remissions (CR, 23%) and two partial remissions (7%)[12, 13]. Incidence of acute and chronic

graft-versus-host disease was 37% and 17%, respectively. Azacitidine and DLI as salvage therapy is safe, induces long-term remission and is today a standard of care for patients in relapse after allo-HSCT [14].

b) VENETOCLAX

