3 HYPOTHESIS

Based on AZARELA trial results, we assume that approximately 30% of responses due to AZA/DLI effects only might be observed. The objective is to demonstrate a 20% increase in response due to the addition of VENETOCLAX (i.e. from 30% to 50% after 6 cycles of AZA/DLI + VENETOCLAX). For the phase I, a design "3+3" will be used including between 9 to 18 patients. For the phase II, a two-stage design will be used. Under $H_0=30\%$ and $p_1=50\%$, the study with $\alpha=0.05$ and $\beta=0.2$, if 3 responses or less are observed in the first 14 evaluable patients, there will be no further inclusions (the inclusions would be terminated early), but all patients on treatment and that continue to derive clinical benefit according to the opinion of the investigator while tolerating study-treatment may continue to receive treatment according to the protocol.

If 4 or more responses are observed, 16 additional patients will be included in the study. If 13 responses or more are observed in evaluable patients, further investigation is warranted to compare AZA/DLI and combination of AZA/DLI and VENETOCLAX. We consider that a maximum of 10% of the population may not be evaluable for response and that a total of 48 patients will be needed to address the question.

All patients on treatment and that continue to derive clinical benefit according to the opinion of the investigator while tolerating study-treatment may continue to receive treatment at the cohort-assigned dose level.

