AEs will be coded using the Medical Dictionary for Regulatory Activities (MedDRA). Incidence tables will be presented for all AEs by maximum grade graded according to the CTCAE, version 5). AEs, SAEs, deaths on study, AEs assessed as related to study drug and AEs resulting in dose reduction, interruption or discontinuation of study drug will be tabulated. Time-to-onset and duration of selected events will also be tabulated.

Laboratory assessments will be presented in shift tables of baseline grade vs. maximum grade on study, and summarized descriptively.

Study Drug Exposure

The number of days and/or cycles that subjects were exposed to study drug will be summarized.

General statistical considerations

Missing values will not be imputed. Outliers will be identified prior to the analyses of the efficacy endpoints and have to be checked by the study physician. According to the decision of the data management, the statistician and the study physician, outliers will be kept in the database or set to "missing".

Analysis datasets

Full analysis set (FAS)

All efficacy analyses will be conducted with the full analysis set (FAS). The full analysis set consists of all patients who were included in the study.

Per protocol analysis set (PPS)

The secondary dataset for analysis is derived from the per-protocol (PP) population. This dataset includes all trial subjects who were treated without major protocol violations.

Safety analysis set

The safety analysis set comprises all trial subjects who received any IMP or other trial treatment.

Sample size calculation

Based on AZARELA trial results, we assume that approximately 30% of responses due to AZA/DLI effects only might be observed. The objective is to demonstrate a 20% increase in response due to the addition of VENETOCLAX (i.e. from 30% to 50% after 6 cycles of AZA/DLI + VENETOCLAX).

For the phase I, a design "3+3" will be used, the number of subjects required for dose escalation will depend upon the occurrence of DLTs as the study progresses. Approximately 9 - 18 subjects may be enrolled to identify the MTD for venetoclax in combination with azacitidine.

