For the phase II, a two-stage design will be used. With the assumption that the AZA/DLI gives 30 % of ORR, with the assumption that AZA/DLI + VENETOCLAX gives 50 % of ORR, and with an alpha risk of 0.05 and a beta risk of 80% with a drop-out of 10%, to confirm the safety and evaluate efficacy, for the phase II, 30 patients should be treated at the optimal dose (27 patients + drop-out of 10%).

Overall, a maximum of 48 patients will be treated: 9 - 18 in phase I and 30 in phase II.

Statistical analysis plan

Analysis will be based on an intent-to-treat basis, whether or not the patient receives the protocol treatment.

It will be performed once the sample size has been reached in each group, separately.

It will be based on the computation of response rate, with 95% confidence interval.

Randomization / Stratification

Not applicable for this trial.

Methods of Statistical analysis

A summary of the planned statistical analyses are described. Structured analyses will be specified in a separate statistical analysis plan (SAP) prior to the end of the data management process and before receiving final study data. If analyses should be conducted deviating from the following descriptions, these deviations also will be specified in the SAP prior to receiving final study data.

Descriptive Statistics

For continuous variables mean, standard deviation (SD), median, interquartile range, minimum and maximum will be presented.

For categorical variables absolute and relative frequencies will be presented.

Interim analysis

An interim analysis is planned during the phase II to evaluate the effectiveness of treatment.

If 3 responses or less are observed in the first 14 evaluable patients, there will be no further inclusions (the inclusions would be terminated early), but all patients on treatment and that continue to derive clinical benefit according to the opinion of the investigator while tolerating study-treatment may continue to receive treatment according to the protocol.

If 4 or more responses are observed, 16 additional patients will be included in the study.

Final analysis

The final report of the study and the compilation of the statistical report will be performed within 12 months after completion and correction of all case report forms (database lock).

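### The phase II decision rule counts evaluable patients, the budget allows 27 and the analysis is declared intent-to-treat; on none of these denominators are alpha 0.05 and 80% power both met

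*Protocol*

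**What the plan says.** Protocol section 10.2 (Sample size calculation) fixes the two rates: "With the assumption that the AZA/DLI gives 30 % of ORR", and "with the assumption that AZA/DLI + VENETOCLAX gives 50 % of ORR". Alpha is 0.05. Section 3 gives beta as 0.2; section 10.2 prints a beta risk of 80%, which can only mean power.

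Three statements then define who is counted.

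- **Decision rule.** The interim rule in section 10.2 reads "If 3 responses or less are observed in the first 14 evaluable patients, there will be no further inclusions". With 4 or more responses, 16 further patients are included. Section 3 adds the final bar of 13 or more responses, again in evaluable patients. Neither section defines evaluable or states a final denominator.
- **Budget.** Section 10.2 says "30 patients should be treated at the optimal dose (27 patients + drop-out of 10"%), and limits phase II to 30 patients and the trial to 48. Section 3 says "We consider that a maximum of 10% of the population may not be evaluable for response".
- **Analysis principle.** Section 10.2 says "Analysis will be based on an intent-to-treat basis, whether or not the patient receives the protocol treatment". It places all efficacy analyses on the full analysis set, meaning all included patients, and also says "Missing values will not be imputed".

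No replacement of non-evaluable patients is described.

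**The concern.** The rule implies 30 evaluable patients, the budget yields 27, and the analysis principle points to everyone included. These are three different denominators for the one decision that phase II exists to make. With a fixed bar of 13 responses, the error rates depend strongly on which is used. If the choice is left until the data are in, who counts as evaluable could change both the interim stop and the final conclusion. Removing patients who were never assessed would favour the treatment if those patients are mostly non-responders.

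**Working it through.** **Inputs.** p0 = 0.30, p1 = 0.50, alpha 0.05, power 0.80, stage 1 of 14 patients stopping at 3 or fewer responses, success at 13 or more (sections 3 and 10.2). Final n is 27 or 30, depending on the reading. Sidedness is not stated. The success rule is one-sided, so I compare it with a one-sided 0.05, the more lenient reading.

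**Formula (exact two-stage binomial).**

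P(success; n, r, p) = Σ over x = 4 to 14 of C(14, x) p^x (1 − p)^(14 − x) × P[Bin(n − 14, p) ≥ r − x]

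**The plan's own figures.** The drop-out step reproduces: 27 / 0.9 = 30. Power at 13 of 30 is 0.814, which matches 80%. Alpha at 13 of 30 is 0.083, which does not match 0.05.

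**Each reading of the denominator.**

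| Reading | Response rates used (p0, p1) | Alpha | Power |
|---|---|---|---|
| 13 of 27 evaluable | 0.30, 0.50 | 0.036 | 0.648 |
| 13 of 30 treated, 10% unassessed counted as failures, 50% read as the rate among assessed patients | 0.30 × 0.9 = 0.27, 0.50 × 0.9 = 0.45 | 0.039 | 0.634 |
| 13 of 30 treated, 50% read as the all-treated rate (the same arithmetic as 30 evaluable) | 0.30, 0.50 | 0.083 | 0.814 |

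**Can another bar rescue it?** Keeping 3 of 14 at stage 1:

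- n = 27: 12 responses give alpha 0.079 and power 0.776; 13 give 0.036 and 0.648.
- n = 30: 13 responses give 0.083 and 0.814; 14 give 0.040 and 0.705.
- With the bar held at 13, alpha stays within 0.05 only up to n = 28 (alpha 0.049, power 0.712), and power reaches 0.80 only from n = 30.

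No threshold at n = 27 or n = 30 meets both targets. An exhaustive search for a Simon two-stage design that does meet them gives a smallest total of 39 patients (stop at 6 or fewer of 19; 16 or fewer of 39 is failure).

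**Reaching 30 evaluable patients.** At 10% loss this takes 30 / 0.9 = 33.3, so 34 patients, above the phase II limit of 30.

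**If non-evaluable patients were dropped and replaced.** This is an assumption, since the protocol describes no replacement. Take 10% loss, all of it among non-responders, and a true all-patient rate of 30%. The rate among evaluable patients is then 0.30 / 0.9 = 0.333.

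- P(success) at 13 of 30: 0.163, against 0.083 with nobody dropped.
- P(interim stop), that is P[Bin(14, p) ≤ 3]: 0.355 at p = 0.30 and 0.261 at p = 0.333.

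Dropping the same patients without replacing them gives 0.079 at 13 of 27.

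**The case against.** Several points on the other side stand.

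- **The 30 is inferred.** Stage 2 says that 16 more patients are included, not 16 evaluable, and no final denominator is printed. That leaves the conflict in place, because the rule still has no stated denominator.
- **The excess alpha is not caused by the mismatch.** The rule 3 of 14 then 13 of 30 has alpha 0.083 even if every patient is evaluable, and falling to 27 lowers alpha to 0.036. Repairing the denominator alone therefore does not restore 0.05.
- **Power is not lost on every reading.** If 50% is the all-treated rate, as the intent-to-treat statement suggests, power at 13 of 30 is 0.81. The figure of 0.63 needs 50% to be the rate among assessed patients.
- **A SAP could define evaluable.** It could, but the protocol itself already fixes incompatible numbers.

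A reader might also infer that about half the patients would leave the denominator. The reference trial reports "A median of three courses AZA", and the first scheduled response marrow here comes after cycle 4. The documents do not support this. Note l of Appendix 1 schedules a marrow at premature termination, and sections 6.8 and 8.8 require end-of-study evaluations for patients who discontinue. Section 24.11.5 classes death during treatment and disease progression as failure in MDS, and section 24.12.2 lists deaths under treatment failure in AML. A median number of courses on a different regimen is not a non-evaluability rate. The only loss figure the protocol gives is a maximum of 10%, so scenarios with much larger losses have no basis in it.

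**Conclusion.** The concern holds as a conflict of denominators. The counting rule, the 27-plus-drop-out budget and the intent-to-treat declaration cannot all be true of the same 30 patients, and the stated pair of alpha 0.05 and power 80% is met under none of them. Depending on the reading, the design has power of about 0.63 to 0.65 with alpha below 0.05, or power 0.81 with alpha 0.083. These figures rest on exact binomial arithmetic from the protocol's own rates and cut-offs. The 0.63 additionally assumes 10% unassessed and 50% as an assessed-patient rate.

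The inflation to 0.16, with the chance of an interim stop falling from 0.36 to 0.26, is conditional. It needs replacement, which the protocol does not describe, and a 10% loss made up entirely of non-responders. It shows why the word evaluable should not stay undefined in the rule; it is not a forecast.

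**What to change.** In sections 3 and 10.2:

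1. Delete evaluable at both decision points. Use the first 14, then all 30 patients treated at the phase II dose. Align the full analysis set and intent-to-treat wording with this; section 8.1 already treats a patient who never starts treatment as a screen failure.
2. Count anyone without a qualifying response assessment, for whatever reason, as a non-responder.
3. Remove the 27-plus-10% drop-out statement, and state that 50% is the all-treated response rate.
4. Restate the operating characteristics. Either keep 13 of 30 and state alpha 0.083 and power 0.81, or use 14 of 30 and state alpha 0.040 and power 0.71. Print the chosen bar and its denominator in both sections.
5. Report an evaluable-patient analysis only as a sensitivity analysis.

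The cost is wording, with no added patients. The observed rate will be lower to the extent that unassessed patients now count as failures. The sponsor must also accept openly either a higher false-positive rate or lower power than now stated. Keeping both stated targets would need at least 39 patients in phase II instead of 30.

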11 BIOLOGICAL STUDY

11.1 *Mutational analysis (Hematology Laboratory, CHRU Lille)*

Mutational screening will be performed by NGS (Illumina platform) and all genes most frequently mutated in myeloid disorders (*TP53, ASXL1, CBL, CEBPA, DNMT3A, ETV6, EZH2, FLT3, IDH1, IDH2, JAK2, KIT, KRAS, MPL, NPM1, NRAS, PHF6, PTPN11, RIT1, RUNX1, SETBP1, SF3B1, SRSF2, TET2, U2AF1, WT1, ZRSR2, CAL-R*) will also be studied. Variant allele frequency (VAF) will be determined for each mutation.

At screening and during follow up (after 4 and 8 cycles and at the end of the study or premature termination) presence of all identified mutations will be investigated with the same technique. All mutation-specific primers and probes will be designed by Biorad (Hercules, CA).

11.2 *Immunologic analysis (Immunology Laboratory, Saint Louis hospital, Paris and INSERM U1065, Mediterranean center of molecular medicine, Nice)*

Sequential phenotypic analysis of NK- and T-cell subsets will be performed on patients with 16-color flow-cytometry. Healthy donors blood samples will be used a control. Supervised analysis on NK cells will include

a study of triggering receptors (NK receptors, activation and proliferation markers) functional proteins (perforin, granzymes, cytokines) whereas T-cell analysis will focus on subpopulations (Th1, Th2, Treg, naïve and memory subsets) and checkpoint receptors (PD-1, CTLA-4, Tim-3, LAG-3, CD96). This work will be coupled to unsupervised dimensionality reduction analysis (t-SNE) and cell-events clustering (SPADE) allowing visualization of complex multi-dimensional data. Such unsupervised analysis will allow identifying non-expected defects in particular subsets, or arrival/disappearance of rare cell subpopulations in patients compared to controls. In function of sample availability and richness, molecular analysis (either on bulk or sorted subsets) could be planned.

12 TREATMENTS

12.1 Treatments Administered

Venetoclax

Venetoclax will be administered at dose levels defined for the cohort a given subject is assigned to at Screening.

Each dose of venetoclax should be taken with approximately 240 mL of water within 30 minutes after the completion of a meal (preferably breakfast). Exceptions may apply if food is not allowed for medical procedures. Tablets must be swallowed whole and must not be broken, chewed, or crushed. The dose should be administered at the same time each day.

On days of concomitant administration of azacitidine, venetoclax should be given prior to azacitidine.

If vomiting occurs after taking venetoclax, do not take any additional dose that day. Take the next dose at the usual time the next day. A missed dose of venetoclax should be taken with food and water within 8 hours of the missed dose. After 8 hours, the missed dose should not be taken. The next dose of venetoclax will be the regularly scheduled dose.

Azacitidine

Azacitidine will be administered at the dose of 75 mg/m²/day for 5 days for each cycle or 50 mg/m²/day for 5 days each cycle if relapse occurred less than 4 months after allo SCT and should be prepared according to the information provided in the Summary of Product Characteristics (SmPC) and will be administered, by IV infusion or SC injection.

12.2 Identity of Investigational Products

Information about the venetoclax and azacitidine formulations to be used in this study is presented below:

Identity of Investigational Products

Study Drug	Formulation	Route of Administration
Venetoclax	10 mg tablet	Oral
Venetoclax	50 mg tablet	Oral
Venetoclax	100mg tablet	Oral

Packaging and Labeling

Venetoclax tablets will be packaged in bottles or blister cards to accommodate the study design. Each bottle or blister card will be labeled per local regulatory requirements. Each tablet contains 10 mg, 50 mg, or 100 mg of venetoclax.

Storage and Disposition of Study Drugs

Venetoclax must be stored at 15° to 25°C (59° to 77°F). The investigational products are for investigational use only and are to be used only within the context of this study. The study drug supplied for this study must be maintained under adequate security and stored under the conditions specified on the label until dispensed for subject use or returned to sponsor.

For more information about Venetoclax, please refer to the IB

Identity of Non-Investigational Products

Study Drug	Formulation	Route of Administration
Azacitidine	100 mg lyophilized powder for injection	SC or IV ^a

a. According to local regulations.

For more information about azacitidine, please refer to SmPC

13 SAFETY AND PHARMACOVIGILANCE

13.1 Adverse Event

An AE is defined as any unintended sign (including an abnormal laboratory finding), symptom, or disease temporally associated with the use of an investigational medicinal product, whether or not considered related to the investigational medicinal product.

In this study, any event occurring after the Study Day 1 and within 30 days of the last study treatment dose of each course should be recorded and reported as an AE. AEs and SAEs occurring after 30 days should only be recorded if considered at least possibly related to study treatment by the local Investigator. Serious and non-serious adverse events occurring after the study-specific informed consent is signed but prior to Study Day 1 will be collected only if they are considered by the investigator to be causally related to the study-required procedures

Laboratory values related to AML, HR MDS and AML, HR MDS progression such as anemia, neutropenia, thrombocytopenia, should not be classified as AEs as long as they are within the expected progression of the disease or expected duration/severity.

The reporting of abnormal laboratory values from unscheduled tests should be avoided unless they lead to clinical consequences or are associated with an AE.

AEs occurring during the study, whether or not attributable to the study treatment, observed by the investigator or reported by the patient spontaneously or in response to a direct question, will be recorded in the patient's source documents as long as they occurred during study treatment administration or within 30 days of last study treatment dose of each course. AEs occurring after 30 days should only be recorded if considered at least possibly related to study treatment by the local Investigator. AEs will be graded in accordance with NCI CTCAE version 5.

For adverse events not captured by the Common Terminology Criteria, the following should be used:

Grade 1: The adverse event is transient and easily tolerated by the subject (mild).

Grade 2: The adverse event causes the subject discomfort and interrupts the subject's usual activities (moderate).

Grade 3: The adverse event causes considerable interference with the subject's usual activities and may be incapacitating (moderate to severe).

Grade 4: The adverse event is life threatening requiring urgent intervention (severe).

Grade 5: The adverse event resulted in death of the subject (severe).

The investigator will document, according to his/her opinion, the relationship of the AE to the study treatment using the criteria outlined in visit schedule (Appendix 1). The nature of each event, start and end date, action taken in response to the event, outcome, NCI CTCAE toxicity grade, relationship to study treatment, and whether the event is serious, should be established and recorded on the AE eCRF. All entries must be clearly documented in the source documents. AEs documented in the eCRF without a stop date should be reviewed at subsequent visits. Documentation on AEs should be updated as necessary. In case of worsening of an AE (i.e. AE grade increase) the event should be captured with the maximal severity observed providing that the AE is ongoing while the AE grade increased.

